5.6. Inclusion Criteria

Patients have to meet the following criteria,

- Men and women aged 18 years or more.
- Newly bacteriologically confirmed TB case (less than a month since diagnosis). This restriction (not more than one month of treatment) does not refer to patients whose most recent treatment outcome was a failure and who were assigned to a new treatment regimen.
- No plans to move out of the clinical settings of the participating TB program sites within 9 months of enrollment.

5.7 Exclusion Criteria

- Pregnancy and any medical condition unrelated to TB will be considered on exclusion grounds.
- Currently enrolled in a clinical trial that prohibits enrollment in another study.
- Patients who are leaving the area within the next six months.
- Previous history of TB, MDR, or extensively drug-resistant (XDR) TB.

5.8 Data Analysis

All analyses were performed using SPSS software, version 28.0 (SPSS Inc., Chicago, IL, USA). *T-test*, $\cong \chi^2$ test, Fisher's exact test, and a logistic regression model were used to determine differences between the intervention group and the control group. According to log-likelihood values, the best fit for the correlation structure was determined to be a compound symmetry structure and random effects were applied to the slope as well as to the intercept. In addition, analysis of variance (ANOVA) was used to determine differences between the two groups based on each monthly accumulated drug adherence rate. Statistical significance was set at $p < 0.05$ (16)

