5.1 Study Design

A longitudinal study design will be adopted to achieve the present study objectives. The study population will be classified with one intervention and one control arm, using a 1:1 allocation ratio, to evaluate whether the intervention is superior to the control treatment will be adopted to achieve the study objectives at General Hospital Penang.

Intervention arm: Enrolled participants will be counseled and educated by a pharmacist on the therapy and benefits of adherence.

Control arm: Enrolled patient will be counseled and educated by the material provided on the therapy and benefits of adherence.

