5.2 Study Setting

The study will be conducted at Hospital Pulau, Penang from November 2022 to November 2023. We will enroll patients with culture-confirmed TB. Additionally, the enrolled PLHIV with any TB symptoms will be investigated with sputum smear microscopy, mycobacterial culture (BACTEC MGIT), Xpert Ultra, and Chest X-ray (CXR). Patients will be eligible for enrolment if they are ≥ 18 years of age, diagnosed with active TB according to national TB program guidelines, had not been previously treated for these diseases, agreed to start treatment for TB, and could give informed consent in either English or Malay.

In Malaysia, a DOT program has been implemented in two phases, “intensive” and “continuation”. In the intensive phase (daily DOT) the current standard anti-TB regimen recommended by WHO

Consists of a 2-month treatment with INH, rifampicin (RIF), pyrazinamide (PZA), and ethambutol(EMB), followed by a 4-month continuation phase with INH and RIF (2EHRZ/4HR) as daily regimen. In the intensive phase (daily DOT), a patient takes their medication in front of the healthcare worker every day at a health facility. In the continuation phase (non-daily DOT), a patient is given the responsibility to take the medication at home and come to a health facility weekly for health checking and medication refilling.

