5.11 Specimen Storage for Future Use

Urine analysis will be discarded immediately after the analysis. No sample will be reused in any further research.

6. Sample Size

The sample size for the current study is based on a statistical superiority trial (continuous data) design of a randomized control trial. Based on the nature of the relevant amount, a superiority design contains statistical superiority trials and clinical superiority trials (9).

$$N = \frac{2 \times Z_{1-\alpha/2}^2 \times (p_0(1-p_0) + p_1(1-p_1))}{d^2} \times S^2$$

Where N is the size per group, p_0 is the response rate of the standard treatment group; p_1 is the response rate of the treatment group; z is the standard normal deviate for a 1 or 2-sided α ; d is the real difference between 2 treatment effect; α a clinically acceptable margin; and S is the Pooled standard deviation of both comparison groups. By following this design and keeping in mind the prevalence of TB

And HIV co-infection in Malaysia, i.e., is 5.9%, the calculated sample size calculated is 382 individuals (191 subjects per arm). We'd need a minimum final sample size of 420 people if we assume a 20% attrition rate (210 per group). All estimates are based on a two-sided test with a significance level of $p < 0.05$.

7. Privacy and Confidentiality

Subject's names will be kept on a password-protected database and will be linked only with a study identification number for this research. The identification number instead of patient identifiers will be used on subject data sheets. All data will be entered into a computer that is password-protected. On completion of the study, data in the computer will be copied to CDs, and the data in the computer erased. CDs and any hardcopy data will be stored in a locked office of the investigators and maintained for a minimum of three years after the completion of the study. The CDs and data will be destroyed after that period of storage. Subjects will not be allowed to view their study data, as the data will be consolidated into a database. Subjects can write to the investigators to request access to study findings.

8. Termination of Study

The researcher/ sponsor may decide to terminate the study at any time. Subjects will be informed if the study is terminated and follow-up visits will be arranged if needed. The criteria for termination depend on unseen circumstances and, the incorporation of the patients.

9. Withdrawal Criteria

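### The one repeated-measures model in section 5.8 names compound symmetry beside a random intercept and slope without placing either, so an arm-by-time test from it may be valid, conservative or anti-conservative

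*Combined protocol and SAP*

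**What the plan says.** Section 5.8 lists a t-test, chi-squared test, Fisher's exact test and logistic regression for comparing the arms. It then states its only model for repeated measurements. In the past tense, and citing log-likelihood, it reports the chosen form as "a compound symmetry structure and random effects were applied to the slope as well as to the intercept". No outcome, time variable, fixed effects, arm-by-time contrast or list of candidate structures is given.

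The next sentence opens a separate analysis: "analysis of variance (ANOVA) was used to determine differences between the two groups based on each monthly accumulated drug adherence rate". Significance is set at p < 0.05, and section 6 adds that the test is two-sided.

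Section 5.4 schedules urine tests at day 0 and at 2, 4 and 6 months, and EQ-5D interviews at the start, at an intermediate point and at month 6. Sections 5.2 and 5.4 describe enrolment and data collection mainly as still to come. Section 6 plans 191 patients per arm before attrition (210 with it), and section 10 analyses only those who stay to the end.

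**The concern.** CS means one variance at all times and one correlation between any two times. A random slope makes both change with time. The sentence names both features without placing either, so two analysts could fit different models and each claim to follow the plan.

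The choice is also presented as an empirical finding about data not yet collected. If an unstructured matrix was among the candidates, the maximised log-likelihood alone could not have favoured CS, which is nested in it. A penalised criterion would be needed, and none is named.

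At stake is the effect of the pharmacist-led intervention on adherence over time (objective 2), and EQ-5D (objective 4) if the model is meant for it. If the placement of CS and the coding of time are left open, they can be settled after the data are seen, and some of those choices do not give a 5% test.

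**Working it through.** The plan gives no error rate for this model beyond the nominal 0.05, so there is no figure of its own to reproduce. I took each reading in turn and then put illustrative numbers on them.

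**Algebra.** Let V be the covariance of one patient's measurements, I the identity, J the all-ones matrix, t the times, Z = [1, t], and G the random-effects matrix.

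- *CS as the whole marginal structure:* V = aI + cJ. A random slope adds terms in t that this form excludes.
- *CS residual plus random intercept:* V = aI + cJ + gJ + slope terms. Only c + g enters V, so the split is not identifiable. V itself and the standard errors of the fixed effects can still be estimated.
- *CS on G:* the intercept and slope variances must be equal. Moving from months to years multiplies the slope variance by 12² = 144, so the constraint cannot hold in both units. The fitted model changes with the unit.

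**Illustration. All of these inputs are assumptions.** The outcome is a running mean of monthly adherence, with patient variance τ² and independent monthly deviations of variance σ². Then

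- Var(month j) = τ² + σ²/j
- Cov(months j, k) = τ² + σ²/max(j, k)

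Data are complete and balanced. Each structure V was fitted to this true covariance S by minimising log|V| + tr(V⁻¹S). With r the ratio of the model SE to the true SE of the linear arm-by-time slope, the type I error is 2[1 − Φ(1.96 r)].

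*Worked case, slope dropped, τ² = σ² = 1, months 1-6.* The variances are 2, 1.5, 1.333, 1.25, 1.2 and 1.167, with mean 1.4083. The mean covariance is 1.2367, so the CS within-patient variance is 1.4083 − 1.2367 = 0.1717. The sum of squares of time is 17.5, so the model variance of a patient slope is 0.1717/17.5 = 0.00981. The true variance is 0.02771. Hence r = √(0.00981/0.02771) = 0.595, and the type I error is 24.4%.

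*Unstructured G.* The model variance of a patient slope is a/17.5 + G₂₂. G₂₂ is free, so the fit matches the true variance: r = 1 and the error is 5.0%.

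Type I error (%) at nominal 5%, for τ²/σ² = 0.43 and 1 (intraclass correlation of monthly values 0.3 and 0.5):

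| Reading | Months 1-6, 0.43 | Months 1-6, 1 | Months 2, 4, 6, 0.43 | Months 2, 4, 6, 1 |
|---|---|---|---|---|
| Unstructured G | 5.0 | 5.0 | 5.0 | 5.0 |
| CS residual, uncorrelated slope | 7.1 | 6.3 | 10.4 | 7.5 |
| CS on G, time in months | 0.0 | 0.0 | 0.3 | <0.1 |
| CS on G, time in days | 0.8 | <0.1 | 0.1 | <0.1 |
| CS on G, time in years | 12.0 | 8.6 | 8.3 | 5.8 |
| CS only, slope dropped | 24.4 | 24.4 | 11.0 | 11.0 |

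Simulation (4,000 runs, months 1-6, ratio 0.43) agrees. CS only gave 25.8% with 191 per arm and 24.2% with 168 (210 × 0.8). Unstructured G gave 5.6% and 5.2%.

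**Sensitivity.** The second row depends on the time origin: in the first column, centring time brings 7.1% back to 5.0%. In the years row, a ratio of 3 gives 4.0% (months 1-6) and 2.3% (months 2, 4, 6). With autoregressive months, CS only reaches 32%.

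**The case against.** The strongest reply is that most statisticians would read the sentence as an ordinary correlated random intercept and slope, perhaps with a superfluous CS residual. On complete balanced data that model holds 5.0% for a linear arm-by-time test even when its covariance is misspecified. This stands. It does not settle the matter, because section 5.8 names CS and never says that the random effects are unstructured.

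Four stronger readings are tempting, and the documents do not support them.

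- *That CS and random slopes flatly contradict each other, so the standard errors are wrong.* This is true only of CS as the marginal structure. CS on the residuals is redundant, and the standard errors can still be valid.
- *That the error rate is 24%.* That figure requires dropping the slope which the sentence names.
- *That the model is meant for accumulated adherence rates.* The plan attaches those to the ANOVA. The running-mean calculation is an illustration, and it does not apply if the model serves a yes/no urine result.
- *That log-likelihood could never select CS.* Candidates are not listed. Against AR(1), which has as many parameters and is not nested with CS, log-likelihood can favour CS.

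Nor does the past tense show that trial data were examined, since the same tense appears for consent in section 5.4. What it shows is that no usable rule for choosing the structure has been written.

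A straight line may also suit adherence poorly, because dosing stops being observed daily after two months: "In the continuation phase (non-daily DOT), a patient is given the responsibility to take the medication at home". That concerns the mean model. It favours categorical visits, but no effect on error was computed for it.

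**Conclusion.** The point holds as one of specification, and it should be fixed before analysis. The sentence does not define a single model. Depending on the reading, CS is incompatible with the slope, redundant, or a constraint tied to the unit of time. A linear arm-by-time test may therefore be valid (5.0%), anti-conservative (about 6-10% with a CS residual and uncorrelated slope, 6-12% with CS on the random effects and time in years) or conservative (about 0% in months, under 1% in days). The 11-24% range arises only if the slope is dropped.

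These figures rest on a running-mean outcome, independent monthly deviations, between-patient to monthly variance ratios of 0.43 to 1, and complete balanced data. None of these is given by the plan for this model, and the figures are not bounds. The conclusions about identifiability and the unit of time are algebraic and do not depend on those assumptions.

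**What to change.** Delete the sentence on CS and random effects, and fix one model per type of outcome in advance.

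- *Continuous repeated outcomes (adherence rate, EQ-5D):* a mixed model with arm, categorical visit, arm-by-visit and, where available, baseline. Use an unstructured within-patient covariance and REML. Name the arm-by-visit contrast to be tested. Also name a simpler structure, with robust standard errors, to be used if the model does not converge.
- *Yes/no urine result:* logistic GEE clustered on patient with robust standard errors, with the equivocal colour assigned to one category in advance.

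The cost is plan wording and some variance parameters. With k visits an unstructured matrix has k(k + 1)/2 of them: 6 for three visits, 10 for four, and 21 if six monthly points are used. That is small at about 191 patients per arm.

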5.9 Statement that collection of specimens

A urine sample is collected for *ISoSreen* Urine analysis to know whether either patient is taking his medication regularly or not. The patient's consent is of utmost important. If patients are comfortable with the collection of samples, then the sample will be collected otherwise the sample will not be collected. An informed consent form translated into both English and Malay will be provided to the patient.

5.10 Rationale for collection of specimens

Treatment adherence for coinfection diseases is difficult due to the complexity, low tolerability, and extended duration of current treatment regimens, especially for both drug-susceptible and drug-resistant TB. As a result, poor adherence raises the chance of treatment failure, relapse, and the development or amplification of drug resistance. Studies have shown rates of non-adherence to be typically 8–33% [5]. The adherence metrics used in research studies and clinical practice have a big impact on the clinical outcomes of the disease. However, near-perfect adherence is required to increase the chances of long-term clinical success. More research is needed on the factors that influence treatment adherence in TB and HIV patients receiving concurrent treatment. As a result, we will undertake a study to learn more about evidence-based adherence and treatment outcomes in TB and HIV patients.

5.11 Specimen Storage for Future Use

Urine analysis will be discarded immediately after the analysis. No sample will be reused in any further research.

6. Sample Size

The sample size for the current study is based on a statistical superiority trial (continuous data) design of a randomized control trial. Based on the nature of the relevant amount, a superiority design contains statistical superiority trials and clinical superiority trials (9).

$$N = \frac{2 \times Z_{1-\alpha/2}^2 \times (p_0(1-p_0) + p_1(1-p_1))}{d^2} \times S^2$$

Where N is the size per group, p_0 is the response rate of the standard treatment group; p_1 is the response rate of the treatment group; z is the standard normal deviate for a 1 or 2-sided α ; d is the real difference between 2 treatment effect; α a clinically acceptable margin; and S is the Pooled standard deviation of both comparison groups. By following this design and keeping in mind the prevalence of TB

And HIV co-infection in Malaysia, i.e., is 5.9%, the calculated sample size calculated is 382 individuals (191 subjects per arm). We'd need a minimum final sample size of 420 people if we assume a 20% attrition rate (210 per group). All estimates are based on a two-sided test with a significance level of $p < 0.05$.

7. Privacy and Confidentiality

Subject's names will be kept on a password-protected database and will be linked only with a study identification number for this research. The identification number instead of patient identifiers will be used on subject data sheets. All data will be entered into a computer that is password-protected. On completion of the study, data in the computer will be copied to CDs, and the data in the computer erased. CDs and any hardcopy data will be stored in a locked office of the investigators and maintained for a minimum of three years after the completion of the study. The CDs and data will be destroyed after that period of storage. Subjects will not be allowed to view their study data, as the data will be consolidated into a database. Subjects can write to the investigators to request access to study findings.

8. Termination of Study

The researcher/ sponsor may decide to terminate the study at any time. Subjects will be informed if the study is terminated and follow-up visits will be arranged if needed. The criteria for termination depend on unseen circumstances and, the incorporation of the patients.

9. Withdrawal Criteria

Subjects can choose to withdraw at any time. Subjects may be withdrawn if the investigator deems that it is detrimental or risky for the subject to continue. As this is a prospective observational study and data in the form of information are only required, the literature suggests about 10-20% dropout or withdrawal has been observed in the past so 20% dropout is already included in the sample size calculation thus the withdrawn subjects will not be replaced with new subjects.

10. Selection of subjects to be included in the analysis

All the subjects who will participate until the end of this study will be included in the final analysis of this study. All subjects who withdraw from the study at any point in time will not be included in the final results analysis.

11. Risk-Benefit Assessment

As stated above, there is no risk from the investigational process and study procedures. No harm could be caused to the patient as there is no invasive procedure involved in the study nor any

Medication is given to the patient. Only non-clinical intervention is given in the study. Study findings shall potentially improve treatment outcomes. The expected benefit outweighs the minimal risk to subjects and thus this study should be supported.

If still any injuries do occur as a direct result of participating in the study, treatment for such injuries shall be provided or paid for by the researcher/ sponsor.

12. Ethics of Study

The study will be conducted in compliance with ethical principles outlined in the Declaration of Helsinki and the Malaysian Good Clinical Practice Guideline.

All aspects of the study protocol, including access to and the use of clinical information of patients, and demographics will get approval by the institutional medical ethics committee locally as well as central health authorities before initiation of this study. Information on individuals will be strictly protected and used for clinical research only.

13. Informed Consent/Assent Process

Patients shall be informed of the study during their usual clinic visits. They will be requested to contact investigators if they are interested. An appointment will be made where the patient information sheet will be provided and explained to them. If they are willing to participate, the consent forms will be signed and dated. If they need to, they are allowed to take the information sheet home to consult with their family members, and another day for getting consent arranged.

14. Conflict of Interest

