3.1 Specific Objectives

1. To perform a systematic review and meta-analysis on evidence-based TB drug adherence.

2. To determine the association between the pharmacist-led intervention and medication adherence level among TB and HIV co-infected patients.
3. To assess the effects of different levels of adherence with therapeutic impact and its possible clinical outcomes.
4. To assess the survival trend with the study population and health-related quality of life (HRQoL) by using the EQ5Dv3 tool.
5. To assess the defaulter patients' approach towards TB and its treatment outcomes.
(Qualitative Approach)

4. Ethical Approval

The study protocols will be approved by the Ethical and Research Committee Ministry of Health, Malaysia. The protocol will also be registered at clinicaltrials.gov

5. Methodology

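### Section 6 does not support 191 per arm: it rests on a co-infection prevalence, gives no response rates, difference, SD or power, and its 420 does not cover 20% attrition

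*Combined protocol and SAP*

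**What the plan says.** Section 6 describes the calculation as "based on a statistical superiority trial (continuous data) design of a randomized control trial". It prints one formula, which has response-rate variances p0(1−p0) + p1(1−p1) multiplied by S² in the numerator, d² in the denominator, and Z(1−α/2) as its only normal deviate. The symbols are explained in words: "p_0 is the response rate of the standard treatment group"; "d is the real difference between 2 treatment effect"; "S is the Pooled standard deviation of both comparison groups". No values follow. The next step is the result, tied only to the prevalence: "HIV co-infection in Malaysia, i.e., is 5.9%, the calculated sample size calculated is 382 individuals (191 subjects per arm".

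Section 6 then asks for "a minimum final sample size of 420 people if we assume a 20% attrition rate (210 per group". On error control it says "All estimates are based on a two-sided test with a significance level of" 0.05. Power is not mentioned in any section.

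The objective that the two-arm comparison serves (Section 3.1) is "To determine the association between the pharmacist-led intervention and medication adherence level among TB and HIV co-infected patients". Section 5.4 measures adherence by self-report, by urine test at day 0 and months 2, 4 and 6, and by refill attendance, and makes none of these primary. Section 5.5, headed as the study end point, gives only the study duration. Section 5.8 lists a t-test, chi-square, Fisher's exact test, logistic regression, a random-effects structure and ANOVA, and again names none as primary. Section 9 says that 20% dropout is already allowed for and that withdrawals are not replaced. Section 10 removes everyone who withdraws from the final analysis.

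**The concern.** A superiority trial is sized from a control value, a target difference, a variance, a significance level and a power. Section 6 supplies only the significance level. The 5.9% describes how common co-infection is in the country. It says nothing about how many patients in either arm will adhere, whichever patients are enrolled.

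Without an outcome, a difference and a power, an ethics committee cannot judge whether enrolling 420 patients is warranted. Nor can a later reader tell whether a null result means no effect or too few patients. The attrition rule adds to this, because the plan's own assumptions bring the analysed number below the figure it says it needs.

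**Working it through.** **Inputs in the plan.** Two-sided α = 0.05 and 20% attrition (Section 6); 1:1 allocation (Section 5.1); 5.9% co-infection prevalence (Section 6). Not given anywhere: p0, p1, d, S, power. Section 5.10 cites 8–33% non-adherence from the literature, but Section 6 does not use it.

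**Attempt to reproduce 191.** The printed formula is N per group = 2 × Z² × [p0(1−p0) + p1(1−p1)] / d² × S². It cannot be evaluated from stated inputs. With S = 1 assumed and d = p1 − p0:

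- 5.9% misread as p0: N = 191 only if p1 = 14.4%. That is 2 × 1.96² × (0.059×0.941 + 0.1438×0.8562) / 0.0848² ≈ 191. The 14.4% appears nowhere in the plan.
- 80% against 90%: 2 × 1.96² × (0.16 + 0.09) / 0.10² = 192.1.
- p0 = p1 = 5.9%: N = 341 at d = 0.05 and 85 at d = 0.10.

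A quite different route also lands there. A single-proportion survey size (p = 0.5, ±5 points), corrected for the 87,581 or 77,903 persons cited in Section 2, gives about 382 in total. That would not be a two-arm power calculation. These are guesses. They show that unrelated designs reach almost the same number, so 191 does not identify the difference sought.

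**Formula type.** For a binary outcome, n per arm = (Z(1−α/2) + Z(1−β))² [p0(1−p0) + p1(1−p1)] / d². For a continuous outcome, n per arm = 2(Z(1−α/2) + Z(1−β))² S² / d². The printed formula multiplies the binary variance by S² and has no Z(1−β), so it is neither.

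**Attrition.**

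- 420 × 0.8 = 336 analysed, 168 per arm, against 382 (191 per arm).
- Needed to keep 382 after 20% loss: 382 / 0.8 = 477.5, so 478.
- Attrition that 420 does cover: 1 − 382/420 = 9.0%.

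**What the planned number could detect (illustration).** Two-sided 5%, 80% power, normal approximation, one time point. The control adherence rates of 67% and 92% are assumed from the 8–33% non-adherence range, and 80% is an assumed value between them.

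- Continuous: (1.96 + 0.8416) × √(2/168) = 0.306 SD. If all 210 per arm were analysed, 0.273 SD.
- Binary, 168 per arm:

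| Assumed control adherence | Detectable rate | Difference (points) | Fisher power at that difference | Difference for 80% Fisher power |
|---|---|---|---|---|
| 67% | 80.3% | 13.3 | 0.759 | 13.9 |
| 80% | 90.7% | 10.7 | 0.761 | 11.1 |
| 92% | 98.4% | 6.4 | 0.741 | 6.7 |

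Fisher powers are by exact enumeration. The adequacy of 191 itself depends wholly on the missing inputs: it gives 18% power for a 5-point gain from 67%, but 78% for a 10-point gain from 80%.

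**The case against.** The best reply is that nothing here shows the size to be wrong. Section 6 only mentions the prevalence on the way to the result and does not say it was substituted for a term. The equation was read from PDF and may be damaged. With S = 1 the printed multiplier, 2 × 1.96² = 7.68, is close to (1.96 + 0.8416)² = 7.85, so the expression would behave much like a binary formula at nearly 80% power. Section 9 gives a dropout range of 10–20%, and at 10% the analysed number is 420 × 0.9 = 378, or 189 per arm, almost the stated 191. Section 5.8 also implies a repeated-measures model, which could change the detectable difference.

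Part of this stands. The formula point is secondary, the detectable differences are illustrations, and falling short of an unsupported 191 does not by itself prove inadequate power.

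The core is untouched. If 5.9% was not an input, then 191 has no effect-size input at all. The prose is intact: it labels the data continuous, defines two response rates and a pooled SD, defines z only for α, and states no power. The near-80% reading needs an S of 1 that the plan does not state. The plan itself adopts 20% attrition, not 10%. The mixed model names no primary outcome, so it does not supply the missing basis.

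**Conclusion.** The concern holds and must be fixed. 191 per arm has no stated basis: 5.9% is not an outcome rate, and p0, p1, d, S and power have no values in any section. The attrition step is wrong on the plan's own figures, since 420 leaves 168 per arm after 20% loss, covers only 9.0%, and would have to be 478 to keep 382. These results need no outside assumption.

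The detectable differences (0.31 SD, or roughly 6 to 13 percentage points) rest on 80% power, a single time point and the assumed control rates. The conclusion is that the size is unjustified, not that it is too small.

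**What to change.** Rewrite the sample-size paragraph in Section 6:

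1. Remove the prevalence as a basis for the size.
2. Name one primary adherence outcome, its time point and its test, and carry the same choice into Section 5.8.
3. Use the one formula that matches (binary or continuous, as given above). If Fisher's exact test is chosen, check the size by exact power.
4. State the control rate or SD with its source, the target difference and the power.
5. Restate what the planned number delivers, for example: *The primary outcome is [adherence measure] at [month], compared by [test]. Assuming [control rate or SD, source], 420 randomised and 168 per arm analysed after 20% attrition give [x]% power at two-sided 5% to detect [difference].*
6. Say plainly that 168 is below 191. If the difference the sponsor considers worthwhile is smaller than the detectable one, report that as a limitation.

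The cost is one paragraph and no added patients. The sponsor must commit to one outcome and test, and the stated detectable difference may look less favourable.

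### The target of 420 allows for about 9% attrition, not the stated 20%: at 20% it leaves 336 evaluable patients (168 per arm) against the 382 (191 per arm) required

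*Combined protocol and SAP*

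**What the plan says.** Section 6 (Sample Size) of the combined protocol and SAP gives the requirement before losses: "the calculated sample size calculated is 382 individuals (191 subjects per arm"). It then allows for losses and says the study would "need a minimum final sample size of 420 people if we assume a 20% attrition rate (210 per group"). Section 5.1 sets the allocation, "using a 1:1 allocation ratio", so the totals divide equally between the arms.

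Two later sections depend on that allowance. Section 9 (Withdrawal Criteria) notes that "the literature suggests about 10-20% dropout or withdrawal has been observed in the past", and concludes that "20% dropout is already included in the sample size calculation thus the withdrawn subjects will not be replaced with new subjects". Section 10, on which subjects are analysed, adds: "All subjects who withdraw from the study at any point in time will not be included in the final results analysis".

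**The concern.** An allowance for 20% attrition should leave the required number once 20% of those enrolled have gone. Going from 382 to 420 adds only 38 patients, about 10% of 382, so the allowance looks roughly half the size claimed.

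The shortfall matters because the plan has no way of absorbing it. Withdrawals are not replaced, and the reason given is that the sample size already allows for 20%. Withdrawals are also left out of the analysis, so each one reduces the analysed sample by one. If attrition reaches the level planned for, the trial ends below its own stated requirement, and the no-replacement rule rests on an allowance larger than the one made.

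**Working it through.** **Inputs, all from the combined protocol and SAP**

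- Required evaluable sample: 382, or 191 per arm (section 6)
- Target after allowing for losses: 420, or 210 per arm (section 6)
- Attrition: 20% (sections 6 and 9); cited range 10-20% (section 9)
- Withdrawals not replaced (section 9) and not analysed (section 10), so evaluable = enrolled × (1 − attrition)
- Allocation 1:1 (section 5.1); two-sided 5% significance level (section 6)

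**Step 1. How 420 arises.** A 10% add-on reproduces it: 382 × 1.10 = 420.2, and per arm 191 × 1.10 = 210.1.

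**Step 2. What 20% requires.** The formula is N enrolled = N required / (1 − attrition).

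- Total: 382 / 0.80 = 477.5, rounded up to 478
- Per arm: 191 / 0.80 = 238.75, rounded up to 239, and 2 × 239 = 478
- Shortfall in the target: 478 − 420 = 58

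The common but incorrect shortcut of multiplying by 1.20 does not give 420 either: 382 × 1.20 = 458.4. Per arm, 191 × 1.20 = 229.2, so 230, or 460 in total.

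**Step 3. What 420 delivers.**

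| Attrition | Evaluable from 420 | Short of 382 |
|---|---|---|
| 10% | 420 × 0.90 = 378 | 4 (1.0%) |
| 15% | 420 × 0.85 = 357 | 25 (6.5%) |
| 20% | 420 × 0.80 = 336 (168 per arm) | 46 (12.0%) |

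The largest attrition at which 382 remain is 1 − 382/420 = 9.05%. This is below the bottom of the range cited in section 9.

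**Step 4. Effect on precision.** The standard error of a difference between two equal arms is proportional to 1/√n. Going from 191 to 168 per arm multiplies it by √(191/168) = 1.066, so confidence intervals are about 6.6% wider.

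**Step 5. Effect on power, on an assumption.** The plan states no power and its printed formula has no power term, so the starting power below is assumed. For a two-sided 5% comparison of two means, take the standardised difference that gives the assumed power at 191 per arm: δ = (1.960 + z) × √(2/191), where z is the normal quantile for that power. Then power at 168 per arm = Φ(δ × √(168/2) − 1.960).

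- If 191 per arm gave 80%: δ = 0.287, and power at 168 is 74.8%
- If 191 per arm gave 90%: δ = 0.332, and power at 168 is 86.0%

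**The case against.** The strongest reply concerns size and framing, since the arithmetic is not in dispute.

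- **The loss may be smaller than 20%.** That value is the top of the range in section 9; at 10% the shortfall is only 4 patients. This stands as a reason to report the whole range. It does not rescue the text, because sections 6 and 9 both name 20% as the value allowed for, and 420 falls short of 382 even at 10%.
- **Some allowance was made.** This is correct: about 10% was added. The fault is that it was described as 20%.
- **The 382 is itself unsupported.** Section 6 gives no values for the response rates, the difference, the standard deviation or the power, so 382 cannot be reproduced. That is a separate problem, and arguably a larger one. The present point takes 382 as the plan's own requirement; any base figure would still need a correct attrition step.
- **The word final in section 6 might mean patients analysed.** If so, enrolment at 20% loss would have to be 420/0.80 = 525, a number the plan never mentions. Section 6 introduces 420 as the result of allowing for attrition, and section 9 says dropout is already covered, so 420 is the number to enrol.

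**Conclusion.** The concern holds and the text is wrong as written. By the plan's own figures, 420 enrolled with 20% attrition gives 336 evaluable patients (168 per arm), 46 fewer than the 382 it says it needs. Across the dropout range the plan cites, the shortfall is 4 to 46. The statement in section 9 that 20% is already covered is incorrect, and so is the reason it gives for not replacing withdrawals.

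This rests on three things the plan states: 382 as the requirement, 20% as the planning value, and withdrawals neither replaced nor analysed. The 6.6% loss of precision follows from the per-arm counts. The power figures are illustrative only, because the plan gives no power.

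**What to change.** Correct section 6 in one of three ways, and make section 9 agree:

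1. State that 420 enrolled (210 per arm) with 20% attrition yields 336 evaluable (168 per arm), and state the difference detectable at 168 per arm.
2. State that 420 supports 382 evaluable only if attrition is at most 9%, and justify that rate against the 10-20% cited in section 9.
3. If 382 evaluable must be kept at 20% attrition, set the target at 478 (239 per arm).

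In section 9, withdraw the claim that 20% is already included unless option 3 is taken, and give the no-replacement rule a basis that does not depend on it.

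Options 1 and 2 are changes of text and need no added patients. Option 1 also requires the sponsor to supply the response rates or standard deviation, the difference and the power, since the plan gives none of them; the resulting detectable difference will be about 6.6% larger than at 191 per arm. Option 3 costs 58 further enrolments.
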